3.2.6. Summary of Anticipated Benefits and Risks

The combination of lenalidomide with SC administration of daratumumab is anticipated to have a positive benefit-risk profile when used for maintenance treatment of patients with newly diagnosed multiple myeloma who are MRD positive and anti-CD38 antibody naïve. Please refer to Section 3.2.1 for additional information. This assessment is based on the following:

• Strategies directed at improving and/or maintaining depth of response are needed to improve clinical outcomes for patients with newly diagnosed multiple myeloma.

- The addition of daratumumab to the standard of care lenalidomide, which is the current a standard of care regimen for maintenance treatment in patients with newly diagnosed multiple myeloma, may improve long-term outcomes through improvement in MRD conversion rate.
- Given the potential advantages of SC administration of daratumumab (refer to Section 3.2.2.2 for detailed information), including shorter time of administration, fewer injection-related reactions, and comparable clinical response rates when compared with administration of daratumumab via IV infusion, the SC route of administration will be used in this study.
- The assessment of primary endpoint of MRD negativity at 12 months post-maintenance will be conducted using a sensitive NGS (sensitivity cutoff of 10⁻⁵) assay (Adaptive Biotechnologies' NGS-based MRD assay), thus providing valuable data on the depth of response achieved with the combination of daratumumab and lenalidomide maintenance treatment in newly diagnosed multiple myeloma patients.
- We expect that the benefits of addition of SC daratumumab to lenalidomide, as maintenance treatment, will outweigh the risks, even among patients who may achieve a CR or better after transplant. As discussed in Section 3.2.1, prolonged administration of daratumumab in conjunction with lenalidomide does not result in an increased total risk of AEs based on data from ongoing trials.
- The potential risks for the study will be mitigated by monitoring via the Independent Data Monitoring Committee and the sponsor's medical monitor during the conduct of the study.

In summary, there is a strong rationale for evaluating SC daratumumab in combination with lenalidomide as maintenance treatment for patients with newly diagnosed multiple myeloma who are anti-CD38 naïve and MRD positive after frontline ASCT.

4. PATIENT POPULATION

Screening for eligible patients will be performed within 60 days before randomization.

The inclusion and exclusion criteria for enrolling patients in this study are described in the following 2 subsections. If there is a question about the inclusion or exclusion criteria below, the investigator must consult with the appropriate sponsor representative and resolve any issues before enrolling a patient in the study. Waivers are not allowed.

4.1. Inclusion Criteria

Each potential patient must satisfy all of the following criteria to be enrolled in the study. Each patient:

- 1. Must be 18 to 79 years of age.
- 1. Must have newly diagnosed multiple myeloma with a history of a minimum of 4 cycles of induction therapy, have received HDT and ASCT within 12 months of the start of induction therapy, and be within 6 months of ASCT on the date of randomization.
- 2. Must have a VGPR or better response assessed per IMWG 2016 criteria at the time of randomization.
- 3. Must have archived bone marrow samples collected before induction treatment (ie, at diagnosis) or before transplant (eg, at the end of induction) or have existing results on the

index MM clone based on Adaptive Biotechnologies' NGS-based MRD assay. Archived bone marrow samples will be used for calibration of myeloma clonal cells to facilitate assessment of the primary end point by NGS. If an existing result on index myeloma clone is available from Adaptive Biotechnologies' NGS-based MRD assay, as part of institutional procedures, an archived bone marrow sample is not required as long as Adaptive Biotechnologies is able to retrieve historical results on the index myeloma clone form the clinical database. Any one of the following archived samples are required:

- a. Greater than 1 mL viable frozen bone marrow aspirated aliquot (preferred) collected in an EDTA tube, frozen, and stored at a temperature of -80°C, or
- b. Non-decalcified diagnostic bone marrow aspirate clot sections (block or slides) for MRD assessment:
- An FFPE block of bone marrow aspirate clot, or slides (preferably 5, if available),
 5 μm each, of non-decalcified bone marrow, or
- ii. Slides (preferably 5, if available), bone marrow aspirate smear,
- iii. Please note, bone marrow core sections are not acceptable samples for analysis.
- iv. In exceptional circumstances when index myeloma clone cannot be identified from the archived bone marrow sample, a post-transplant sample can be used to identify myeloma clone with permission from the Sponsor.
- 4. Must have residual disease as defined by detectable MRD (Adaptive Biotechnologies' NGS-based MRD assay). If this assay was conducted post ASCT as part of institutional procedures and MRD results are available during screening, then patients who were MRD positive at 10⁻⁵ based on the existing NGS test result are also eligible to participate in the study (such patients will NOT be required to undergo MRD assessment by NGS again at the time of screening).
- 5. Must have an ECOG performance status score of 0, 1, or 2 (see Section 9.2.1).
- 6. Must have pretreatment clinical laboratory values meeting the following criteria during screening (laboratory tests should be repeated if not done within 3 days of C1D1):

Adequate bone marrow function:

- a. Hemoglobin ≥7.5 g/dL (≥4.65 mmol/L). Prior red blood cell (RBC) transfusion or recombinant human erythropoietin use is permitted, however transfusions are not permitted within 7 days of randomization to achieve this minimum hemoglobin count.
- b. Absolute neutrophil count $\geq 1.0 \times 10^9$ /L. Granulocyte colony stimulating factor use is permitted.
- c. Platelet count $\geq 75 \times 10^{9}$ /L for patients in whom < 50% of bone marrow nucleated cells are plasma cells. Otherwise, $\geq 50 \times 10^{9}$ /L (transfusions are not permitted within 7 days of testing to achieve this minimum platelet count).

Adequate liver function:

- a. Aspartate aminotransferase ≤ 2.5 folds of the upper limit of normal (ULN).
- b. Alanine aminotransferase ≤ 2.5 folds of the ULN.

c. Total bilirubin ≤2.0 folds of the ULN (except in patients with congenital bilirubinemia, such as Gilbert syndrome, direct bilirubin ≤2.0 folds of the ULN)

Adequate renal function:

- a. Estimated creatinine clearance ≥30 mL/min. Creatinine clearance may be calculated using Cockcroft-Gault, estimated glomerular filtration rate (Modification of Diet in Renal Disease [MDRD]), or Chronic Kidney Disease Epidemiology Collaboration (CKD-EPI) formula; refer to Section 9.2.2.
- b. Corrected serum calcium $\leq 14 \text{ mg/dL}$ ($\leq 3.5 \text{ mmol/L}$) or free ionized calcium $\leq 6.5 \text{ mg/dL}$ ($\leq 1.6 \text{ mmol/L}$); refer to Section 9.2.3.
- 7. If a female:
 - a. Must not be of childbearing potential: defined as premenarchal; postmenopausal (>45 years of age with amenorrhea for at least 12 months or any age with amenorrhea for at least 6 months and a serum follicle stimulating hormone level >40 IU/L); permanently sterilized (eg, bilateral tubal occlusion [which includes tubal ligation procedures as consistent with local regulations], hysterectomy, bilateral salpingectomy, bilateral oophorectomy); or otherwise be incapable of pregnancy.

or

- b. If of childbearing potential:
 - i. Must commit to either abstain continuously from heterosexual sexual intercourse or to use 2 methods of reliable birth control simultaneously during the treatment period.

Sexual abstinence is considered a highly effective method only if defined as refraining from heterosexual intercourse during the entire period of risk associated with the study drug.

Methods of reliable birth control include 1 highly effective form of contraception (tubal ligation, intrauterine device, hormonal [birth control pills, injections, hormonal patches, vaginal rings, or implants], or partner's vasectomy) and 1 additional effective contraceptive method (male latex or synthetic condom, diaphragm, or cervical cap).

Contraception must begin 4 weeks prior to dosing.

Reliable contraception is indicated even where there has been a history of infertility, unless due to hysterectomy or bilateral oophorectomy.

and

ii. Must have 2 negative serum or urine pregnancy tests during screening, first within 10 to 14 days prior to dosing and the second within 24 hours prior to dosing.

and

iii. Must agree not to donate eggs (ova, oocytes) for the purposes of assisted reproduction during the study and for 4 weeks after the last dose of lenalidomide and for 3 months after the last dose of daratumumab

- 8. If a man who is sexually active with a female of childbearing potential:
 - a. Must agree to use a latex or synthetic condom, even if he had a successful vasectomy. and
 - b. Must agree to not donate sperm during the study and for 4 weeks after the last dose of lenalidomide and for 3 months after the last dose of daratumumab.
- 9. Must sign (or have his/her legally acceptable representative sign) an informed consent form (ICF) indicating that he or she understands the purpose of and procedures required for the study and is willing to participate in the study.
- 10. Is able, and agrees, to the prohibitions and restrictions specified in this protocol.

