- 4. Have archived bone marrow samples collected before induction treatment (ie, at diagnosis) or before transplant (eg, at the end of induction) or have existing results on the index MM clone based on Adaptive Biotechnologies' NGS-based MRD assay. Archived bone marrow samples will be used for calibration of myeloma clonal cells to facilitate assessment of the primary endpoint by NGS. Any one of the following archived bone marrow samples are required:
 - Greater than 1 mL viable frozen bone marrow aspirated aliquot (preferred) collected in an ethylenediaminetetraacetic acid tube, and stored at a temperature of -80° C, or
 - Non-decalcified diagnostic bone marrow aspirate clot sections (block or slides) for MRD assessment:
 - A Formalin fixed paraffin embedded (FFPE) block of bone marrow aspirate clot, or slides (preferably 5 slides, if available), 5 µm each, of non-decalcified bone marrow, or
 - Slides (preferably 5 slides, if available), bone marrow aspirate smear.
 - Please note: bone marrow core sections are not acceptable samples for analysis.
 - In exceptional circumstances when index myeloma clone cannot be identified from the archived bone marrow sample, a post-transplant sample can be used to identify myeloma clone with permission from the Sponsor.
 - If an existing result on index myeloma clone is available from Adaptive Biotechnologies' NGS-based MRD assay, conducted as part of institutional procedures, then archived bone marrow sample is not required as long as Adaptive Biotechnologies is able to retrieve historical results on the index myeloma clone from the clinical database.
- 5. Have residual disease as defined by detectable MRD by NGS (Adaptive Biotechnologies' NGS-based MRD assay). If this assay was conducted post ASCT as part of institutional procedures and MRD results are available during screening, then patients who were MRD positive at 10⁻⁵ based on existing NGS test result are also eligible to participate in the study (such patients will NOT be required to undergo MRD assessment by NGS again at the time of screening),
- 6. Be anti-CD38 treatment naïve.

DOSAGE AND ADMINISTRATION

The 2 treatment arms comprise of daratumumab in combination with lenalidomide or lenalidomide alone as follows (each treatment cycle will be 28 days, with a maximum duration of maintenance treatment of 36 cycles):

- 1. Daratumumab 1800 mg administered by SC injection:
 - Weekly during C1 and C2,
 - Every 2 weeks during C3 to C6, and

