MRD (aspirate) by NGS	X (NGS)	At the end of 12, 18, 24, and 36 months (NGS), (ie, C13D1, C19D1, C25D1 and at the EOT visit)	X		 During Screening: NGS assay (Adaptive Biotechnologies' NGS-based MRD assay) to be done on bone marrow aspirate collected during screening to determine eligibility for study entry. Residual samples, if available, will also be banked for future tests. Two sequential NGS assays will be done during screening. The first NGS assay will be conducted on archived bone marrow samples for calibration and identification of the index myeloma clone. Obtain archived bone marrow samples as described in Inclusion Criterion #4. If an existing result on index myeloma clone is available from Adaptive Biotechnologies' NGS-based MRD assay, conducted as part of institutional procedures, then archived bone marrow sample is not required as long as Adaptive Biotechnologies is able to retrieve historical results on the index myeloma clone from the clinical database. Following index clone calibration (or verification of existing index clone results from a previously conducted Adaptive Biotechnologies' NGS-based MRD assay), MRD will be assessed by NGS (Adaptive Biotechnologies' NGS-based MRD assay), using fresh bone marrow aspirate sample collected during screening. Note: If Adaptive Biotechnologies ' NGS- based MRD assay was conducted post-ASCT as part of institutional procedures and MRD results are available at screening, these results are to be recorded in the eCRF. Patients who are MRD positive at 10⁻⁵ based on an existing post-ASCT NGS assay conducted by Adaptive Biotechnologies, are eligible to participate. Such patients will not be required to undergo NGS based MRD assessment again during screening. After the start of study treatment (after C1D1):
-----------------------	---------	--	---	--	---

		STUDY PHA			
PROCEDURE	SCREENING	Maintenance (Cycles 1–36)	ЕОТ	Follow-up (from the date of last study treatment until the end of study)	Notes
					 NGS is to be conducted at 12, 18, 24, and 36 months: During the bone marrow aspirate procedure, the first aspirate sample that is drawn will be sent to the central laboratory to determine MRD by NGS. All bone marrow aspirates to be sent to the central laboratory should be at least 3 mL. Additional bone marrow aspirate samples may be taken and used for local laboratory testing. Bone marrow aspirate collected within ±30 days of the scheduled visit during the maintenance phase is acceptable.

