1. INTRODUCTION

Despite advances in treatment, multiple myeloma remains a challenging disease to cure. The addition of the anti-CD38 monoclonal antibody (mAb), daratumumab, to standard of care regimens has been associated with a 44% to 68% significant reduction in the risk of death or progression in multiple myeloma compared with standard of care, as observed in 5 randomized controlled studies: the POLLUX and CASTOR Phase 3 clinical studies in relapsed or refractory myeloma and the ALCYONE, CASSIOPEIA^{16,29}, and MAIA Phase 3 clinical studies in newly diagnosed myeloma. Recently, daratumumab was approved in combination with bortezomib, melphalan, and dexamethasone for frontline treatment of newly diagnosed multiple myeloma patients who are ineligible for transplant. Maintaining remission and improving the duration of response after successful induction, high-dose therapy (HDT) followed by autologous stem cell transplant (ASCT) and consolidation therapy are important goals in treating patients with newly diagnosed multiple myeloma.¹

Despite these treatment modalities, most multiple myeloma patients relapse after ASCT. Conventional means of assessing response (ie, measurement of serum and urine M-proteins) are not sufficiently sensitive to measure low-levels of residual bone marrow disease or minimal residual disease (MRD), and the attainment of MRD negativity (ie, MRD is not detectable by highly sensitive next generation flow [NGF] cytometry of sequencing) is associated with improved long-term outcomes. Therefore, achievement of MRD negativity is evolving as an important clinical efficacy endpoint in multiple myeloma, particularly in the maintenance setting following frontline ASCT.

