3.2.5. MRD Assessment Using NGS

The most commonly used sensitive methods to monitor MRD include allele-specific oligonucleotide polymerase chain reaction (PCR) and multiparametric flow cytometry (MFC).^{38,40} Each method offers distinct advantages and disadvantages. The MFC has been widely applied in the diagnostic and prognostic evaluations of patients with myeloma and may have value in response assessment, particularly in the context of patients undergoing ASCT.^{36,40} The Adaptive Biotechnologies' NGS-based assay approved by the Food and Drug Administration (FDA) for assessment of MRD in acute lymphoblastic leukemia or multiple myeloma, is the most sensitive validated assay available with the ability to detect one malignant cell in the background of a million normal cells.

In this study, MRD will be assessed using Adaptive Biotechnologies' NGS-based MRD assay for rapid determination of study participation eligibility during screening. Residual samples collected during screening will also be banked for future tests. Two sequential NGS assays will be conducted

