5.2.1. Definition

The primary endpoint of this study is the MRD conversion rate from baseline to 12 months after start of maintenance treatment. It is defined as the proportion of subjects who were MRD [at 10⁻⁵] positive at baseline and have achieved MRD negative status [at 10⁻⁵] as determined by NGS by 12 months of maintenance treatment. The primary endpoint will be analyzed based on FAS.

Subjects' MRD positive status at baseline should be verified. Since subjects do not always adhere to the protocol visit schedule, the post-baseline MRD records from randomization up to 12-month + 2 months will be selected for MRD negativity status evaluation. Subjects with missing or unevaluable MRD status will be considered as MRD positive. Subjects who have achieved MRD negative status on or after PD or switch to subsequent anti-myeloma therapy before PD, will not be considered MRD negative in the primary endpoint analysis.

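### Eligibility sets no 10⁻⁵ threshold for a fresh screening sample, so a patient already below the endpoint cutoff can be randomised, stays in the FAS and cannot count as a converter

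*Protocol*

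**What the plan says.** Section 4.1 of the Protocol prints the MRD requirement as criterion 4. The Synopsis (Patient Population) and Section 3.1 repeat it as item 5. It has two routes.

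- **Fresh screening sample.** Section 4.1 asks for "Must have residual disease as defined by detectable MRD" and the copies say "Have residual disease as defined by detectable MRD by NGS". No threshold is attached. The MRD row of the Time and Events Schedule Part 1 says the assay is "to be done on bone marrow aspirate collected during screening to determine eligibility for study entry", again without a number. Schedule Part 2 and Sections 3.2.5 and 9.3.4 add none for the fresh sample.
- **Existing post-ASCT result.** Patients who were positive at 10⁻⁵ "based on the existing NGS test result are also eligible to participate in the study" and need no repeat test.

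Section 3.2.5 credits the assay with the "ability to detect one malignant cell in the background of a million" normal cells. SAP 5.2.3 lists MRD negativity at 10⁻⁶ among its supplemental analyses.

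SAP 2.3.1 defines the FAS as everyone randomised, and SAP 5.2.1 uses it for the primary endpoint. SAP 5.2.1 counts a subject who was, at 10⁻⁵, "positive at baseline and have achieved MRD negative status" at the same level. It asks that baseline positivity be verified, but not that failures be counted. SAP 5.2.2 describes the estimand population as positive at 10⁻⁵. Protocol 11.3.1 speaks of conversion from baseline, but its counting rule names only the later negative result.

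**The concern.** Eligibility, endpoint and estimand should share one cutoff. Here the endpoint and the estimand use 10⁻⁵, and one of the two entry routes does not. A patient whose fresh sample reads, say, 5×10⁻⁶ can be enrolled with the criterion followed exactly. That patient enters the denominator and can never be a success under SAP 5.2.1.

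Three things are at stake: some power, slightly lower conversion rates in both arms, and an analysed population wider than the one the estimand names. No planned analysis would isolate the effect. The MRD-evaluable set in SAP 2.3.1 needs only a baseline assessment and one later one, so it keeps these patients. The plain negativity rate at 10⁻⁵ in the FAS (SAP 5.2.3) might partly reveal them, but it is optional.

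**Working it through.** **Inputs.** From Protocol 11.2 and SAP 1.4: 107 per arm, 20% vs 40%, two-sided alpha 0.05, continuity-corrected chi-squared, power at least 85%. From SAP 5.2.3: stratified CMH for the comparison, with a p-value from Fisher's exact test. The share f of randomised patients below 10⁻⁵ at baseline is an assumption, because the documents do not give it. Cytogenetic strata are ignored because their sizes are not given.

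**Step 1: the plan's own figure.** With n per arm, d the difference and p̄ the mean rate:

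power = Φ{[d − 1/n − 1.96·√(2p̄(1−p̄)/n)] / √([p₁(1−p₁)+p₂(1−p₂)]/n)}

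At n = 107, p₁ = 0.20, p₂ = 0.40: (0.2000 − 0.0093 − 1.96×0.0627)/0.0611 = 1.11, so power is 86.6%. Exact binomial enumeration gives 86.7%. The stated 85% is met.

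**Step 2: rates with a share f below the cutoff.** Under SAP 5.2.1 these patients cannot succeed, so each arm's rate becomes p(1−f). At f = 10% this is 18% vs 36%, and the odds ratio is (0.36/0.64)/(0.18/0.82) = 2.56. The planned value is (0.40/0.60)/(0.20/0.80) = 2.67.

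**Step 3: power, exact enumeration, 107 per arm.**

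| f (patients of 214) | Rates | Odds ratio | Corrected chi-squared | Fisher | CMH, unstratified |
|---|---|---|---|---|---|
| 0 | 20% vs 40% | 2.67 | 86.7% | 87.1% | 89.9% |
| 5% (about 11) | 19% vs 38% | 2.61 | 84.1% | 84.5% | 87.8% |
| 10% (about 21) | 18% vs 36% | 2.56 | 81.1% | 81.4% | 85.3% |
| 20% (about 43) | 16% vs 32% | 2.47 | 74.0% | 74.2% | 79.4% |

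The formula in step 1 gives 80.8% at f = 10%, in line with the corrected chi-squared column.

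**Step 4: a set restricted to patients positive at 10⁻⁵.** The rates return to 20% vs 40% and the odds ratio to 2.67. With 102, 96 or 86 per arm, power is 85.4, 83.0 or 78.2% (corrected chi-squared) and 88.5, 86.6 or 82.8% (CMH).

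**Step 5: Protocol 11.3.1 read literally.** If a patient already below 10⁻⁵ counted as a success and stayed negative, the rates at f = 10% would be 0.9×20% + 10% = 28% and 0.9×40% + 10% = 46%. Power by the step 1 formula would be 73.8%. The two counting rules therefore give different answers for the same patient.

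**The case against.** The strongest reply is that the SAP already sets the handling. SAP 5.2.1 with the FAS makes such a patient a non-converter by a pre-specified, conservative rule that is the same in both arms. That stands, and it limits the point to eligibility and reporting. It also means that repeating the baseline condition in the lead-in of SAP 5.2 or in the estimand variable would be drafting only. The lead-in sits directly above the full definition, and the estimand carries the condition in its population attribute.

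A second reply is that 10⁻⁵ is the intended cutoff throughout. Protocol 3.2.6 says the 12-month assessment is "conducted using a sensitive NGS (sensitivity cutoff of" 10⁻⁵, and several sections require patients to be MRD positive at screening. Section 4 also sends questions about the criteria to the sponsor before enrolment. This makes a 10⁻⁵ reading of both routes plausible but does not establish it. Section 3.2.6 concerns the endpoint, the Introduction explains negativity as "MRD is not detectable by highly sensitive next generation flow" cytometry or sequencing without a number, and criterion 4 gives the number for one route only.

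Third, nothing shows that any such patient exists. That is correct, so the power table cannot serve as evidence of harm. The restricted analysis also recovers little: about 1 to 4 points of power over the range shown, and an odds ratio of 2.67 instead of 2.56 at f = 10%.

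**Conclusion.** The gap is real and minor. Criterion 4, followed exactly, can admit a patient who cannot meet the endpoint and who is outside the estimand population. Its size depends wholly on f, which is unknown. At f = 0 there is no effect. At an assumed 10%, power would be about 81% with the planning test and about 85% with an unstratified CMH test.

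A reader might infer four stronger things, and the documents support none of them.

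- **That the trial is underpowered.** The planned figure reproduces, and any loss is conditional on f.
- **That the comparison is biased or type I error inflated.** Baseline level is fixed before randomisation, so the dilution falls on both arms alike.
- **That the 20% and 40% planning rates are wrong.** Nothing here contradicts them for a population positive at 10⁻⁵.
- **That patients already below the cutoff will be counted as successes.** Only a literal reading of Protocol 11.3.1 allows this. SAP 5.2.1 excludes it, and Protocol Section 11 leaves the specific details to the SAP.

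**What to change.** 1. For any patient still to be enrolled, require positivity at 10⁻⁵ on both routes in Protocol 4.1 criterion 4 and its copies in the Synopsis and Section 3.1. The cost is slightly stricter screening. The documents do not state enrolment status. The follow-up provisions for patients who have finished 36 cycles suggest a late stage, so this item may have no effect.
2. In the SAP, report by arm the number of randomised subjects not positive at 10⁻⁵ on the pre-randomisation NGS result used for eligibility, whether fresh or existing. Add one supportive analysis of the primary endpoint restricted to subjects positive at 10⁻⁵ on that result. Use the eligibility result and not the general baseline of SAP 2.6, which runs to first dose and so may fall up to 3 business days after randomisation. Restricting on a pre-randomisation value does not bias the comparison. The cost is one count, one table and a slightly smaller set.
3. Make the counting rule in Protocol 11.3.1 match SAP 5.2.1 by adding the baseline condition at 10⁻⁵. The cost is one sentence.
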